8.1. Study Risks

Adverse effects (rare events overall <2%) include irritation, redness, itchiness, discomfort, infection, and allergic reaction. Subjects will be closely monitored for all side effects. For side effects/adverse events, patients will be treated with standard medical care to address their symptoms. The arm that they are enrolled in will not influence treatment.

8.2. Randomization Risk

Since wound closure will be randomized, it is possible that the patient may be in a group with higher adverse outcomes.

8.3. Loss of Confidentiality

Any time information is collected there is a potential risk for loss of confidentiality. Every effort will be made to keep patient's information confidential; however, this cannot be guaranteed.

9. Subject Safety and Data Monitoring

The PI and research staff will be responsible for monitoring the safety of this study. A report to the IRB will be submitted according to its policy if adverse events (AEs) or serious adverse events (SAEs) occur, and any changes in the protocol as a result of these events. No interim analysis will be planned and there will be no study-specific criteria to halt the study. Since, Monocryl and INSORB absorbable stables are deemed safe and available for use according to the FDA, there are no safety and minimal toxicity concern.

The research staff will ensure all aspects of data quality including monitoring for adherence to consent procedures, inclusion and exclusion criteria, valid abstraction, correct entry, timeliness and responsiveness to data queries.

Data collection will take the form of excel data entry and will be identified with a participant ID number. Data will be collected and stored with the participant ID code only. The master enrollment log linking patient identifiers with study ID numbers will be kept in a password-protected database on the Ob/Gyn Department's internal server separate from the data. Several data collection forms will be used. Data on these forms devoid of personal identifiers will be securely stored at our perinatal research division. The research staff will be available to monitor the data and correct any discrepancies based on source documents if needed. The principal investigator and research staff will monitor the study accrual rate, study attrition including withdrawals/dropouts, and any changes in risk/benefit bi-annually.

Each subject will be provided contact information to reach study staff. Additionally, the consent form provides instructions and a mechanism of contact for subjects to reach the primary investigator and also provides contact information for the subject to contact the IRB directly. Any significant concerns or complaints or requests for study information would be directed from the study staff to the study coordinator and study PI. Any complaints or adverse events gleaned from these contacts would be reported to the IRB (per IRB policy) and to the sponsor.

10. Procedures to Maintain Confidentiality

Each patient will be assigned a study number with personal identifiable information deleted or removed. Subjects' information will be de-identified and tagged with a number. Data will be collected and stored on a UTMB password-protected computer in a locked room.

The data collected will be kept on a password-secured UTMB computer. An encrypted USB flash drive will be used to transfer data. The data will be linked to the subject by subject's MRN number. This identifier is needed to access and analyze demographic data. During analysis of the data, all identifiers will be deleted.

11. Potential Benefits

A potential benefit is that the novel stapler device leads to shorter operating room time, better aesthetic outcomes, improved patient satisfaction, and less pain. We also hope that this novel stapler will ultimately reduce SSI rates and maternal health costs.

12. Statistical Approach

Analysis will be performed by intent to treat. For this analysis, normality will be tested using Shapiro-Wilk method. Between-group differences in continuous variables will be assessed using Student t test or Man-Whitney rank sum test and results will be given as mean, standard deviation, or median range as appropriate. Categorical variables will be assessed using the Pearson chi-square test or Fisher exact test as appropriate. For dichotomous endpoints, relative risk (RR) and 95% CI values will be calculated. P < 0.05 will be considered significant. The analysis will be performed after study completion.

Sample size was calculated based on the determination of superiority. The primary outcome is operative time in minutes. Based on our institution's usual operating time for a routine cesarean section, the mean of operative time in patients undergoing incision closure with sutures was 55.46 with a standard deviation of 13.63 mins. We estimated that the absorbable staples would lead to a decrease in time by 5 mins. If we calculate the sample size based on 90% power to confirm superiority and an alpha of 0.05, we estimate we would need a total of 316 patients. Assuming a 10% loss to follow-up, we plan to enroll a total sample size of 352 (176/group). STATA 16 (Dallas, TX) will be used for statistical computations. This trial will be registered with Clinical Trials Register (Clinicaltrials.gov), before recruitment is initiated and after IRB approval.

Below is the sample size calculation protocol:

T tests - Means: Difference between two independent means (two groups)

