6.6. Primary Outcome

OR Case time in minutes

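### The trial is sized on a 5-minute difference in mean operative time, but section 12 does not commit the primary analysis to that difference or plan a 95% CI for it

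*Combined protocol and SAP*

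**What the plan says.** Section 6.6 (Primary Outcome) gives only "OR Case time in minutes". Section 12 (Statistical Approach) repeats the outcome as "The primary outcome is operative time in minutes" and sizes the trial on it. The suture mean is 55.46 min with SD 13.63, and "We estimated that the absorbable staples would lead to a decrease in time by 5 mins". The sample size output is headed "T tests - Means: Difference between two independent means (two groups". It is two-sided, with alpha 0.05 and 90% power.

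The analysis paragraph of section 12 has no statement specific to the primary outcome. Operative time falls under the general rule for continuous variables:

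- "normality will be tested using Shapiro-Wilk method"
- "Between-group differences in continuous variables will be assessed using Student t test or Man-Whitney rank sum test"
- "results will be given as mean, standard deviation, or median range as appropriate"

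Confidence intervals appear once, for another type of endpoint: "For dichotomous endpoints, relative risk (RR) and 95% CI values will be calculated".

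**The concern.** The sizing and the analysis are not bound to the same quantity. The sizing concerns a difference in means, in minutes. The analysis paragraph allows either a comparison of means or a rank test, and it does not say which applies to operative time. The normality test has no other stated purpose, so it presumably makes the choice from the trial's own data. Its significance level, whether it is applied by arm or to pooled data, and what result triggers a switch are all unstated.

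No between-group difference in minutes is planned for the primary outcome, and no interval for one. If the rank-sum route is taken, the primary result as planned would be a p value with two medians and two ranges. A reader could not set that against the 5-minute target with any measure of uncertainty.

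**Working it through.** **Inputs.** From section 12: suture mean 55.46, SD 13.63, reduction 5 min, two-sided alpha 0.05, power 90%, 158 per arm evaluable (316), 176 per arm enrolled (352). The documents do not give the shape of the operative-time distribution or the switching rule, so both are assumed below.

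**1. The plan's own figure reproduces.**
- d = 5/13.63 = 0.36684.
- Noncentrality = d × √(n/2) = 0.36684 × √(158/2) = 3.2605. The critical t on 314 df is 1.96755.
- Power is 0.9016 with 158 per arm and 0.8998 with 157, so 158 is the smallest n that reaches 90%.
- Per arm, 158/0.90 = 175.6, rounded up to 176, which gives 352.

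The sample size is correct for a t test on means.

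**2. What that t test would deliver.** The 95% CI half-width is t(0.975, 2n−2) × 13.63 × √(2/n).
- n = 158: SE 1.533, half-width 1.9675 × 1.533 = 3.02 min.
- n = 176: SE 1.453, half-width 1.9668 × 1.453 = 2.86 min.

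An observed 5-minute reduction with 158 per arm would be reported as 5 ± 3.0, about 2.0 to 8.0 min.

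**3. How often a normality rule would move the analysis off the mean.** There were 4,000 simulated trials per setting, with suture mean 55.46, staple mean 50.46 and SD 13.63 in both arms. The staple arm was built in two ways: the same family at its own mean, or the suture distribution shifted by −5. Ranges cover both. Shapiro-Wilk is taken at 0.05.

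With CV = 13.63/55.46 = 0.246 (suture) and 13.63/50.46 = 0.270 (staple), gamma skewness is 2·CV = 0.49 and 0.54. Lognormal skewness is 3·CV + CV³ = 0.75 and 0.83.

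| Assumed shape | Either arm rejects, 158/arm | Either arm rejects, 176/arm | Pooled test, both sizes |
|---|---|---|---|
| Normal | 9.1–9.5% | 9.7% | 4.6–4.9% |
| Gamma | 83.3–87.0% | 87.6–90.8% | 85.4–93.4% |
| Lognormal | 98.9–99.3% | 99.5–99.6% | 99.4–99.8% |

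A repeat simulation at 158 per arm gave 10%, 87% and 99% for the either-arm rule.

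**4. Is the switch needed for validity?** At 158 per arm, over the same three shapes:
- t test on means: power 0.893–0.898, type I error 0.046–0.052, CI coverage 0.947–0.954.
- Two-step rule: power 0.894 (normal), 0.910 (gamma) and 0.925 (lognormal), type I error 0.047–0.052.

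The t test is sound at this sample size without a normality check. The two-step rule does no harm to error rates. With equal arms the Student and Welch statistics coincide and only the degrees of freedom differ.

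**5. What can be recovered from each route.**
- t-test route: means, SDs and group sizes are reported, so a reader can derive the difference and its CI as in step 2.
- Rank-sum route: the difference in medians can be read off. The mean difference cannot, and a range does not yield a standard error for either quantity. The difference in medians is also the noisier estimate: its simulated standard deviation was 1.87 min under gamma and lognormal shapes, against a standard error of 1.53 min for the difference in means.

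**The case against.** The strongest reply is that little would change in practice. Error rates and power are preserved, and the two-step rule is slightly more powerful under skewness. Under a pure shift the mean and median differences are both 5 min. With each arm keeping its own gamma or lognormal shape, the true median difference is about 5.1 min. In simulation with 158 per arm, the Welch t and rank-sum tests reached the same verdict at 0.05 in 97% of gamma trials and 95% of lognormal trials. The switching percentages therefore show how often the method changes, not how far the answer moves. This stands for the shapes examined. It need not hold if staples mainly shorten the longer cases, where mean and median effects could separate.

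A second reply is that the switching rule is inferred and the skewed shapes are assumed. Section 12 never says that a rejected normality test forces the rank-sum test, and with normal times the switch rate is only 5–10%. That is correct, so the percentages are illustrations. If the inferred rule is wrong, however, the choice of test is less constrained still.

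Third, the sizing makes the comparison of means the evident default, and nothing rules out reporting a CI. But a planning assumption does not bind the analysis, and the analysis paragraph expressly allows another test.

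Finally, a rank test with a Hodges-Lehmann shift and its CI, fixed in advance, would also close the gap. This is true: the defect is the lack of commitment, not the rank test itself. The difference in means is preferred because it is the quantity the trial was sized on.

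**Conclusion.** The concern holds. Section 12 assigns no single test or effect measure to the primary outcome and plans no difference in minutes with a 95% CI, although the trial is sized on a 5-minute difference in means. The cost falls on the quantity estimated and its precision, not on type I error or power, and the sample size needs no correction.

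How likely the rank-sum route is depends on the unknown distribution and on an inferred rule: about 5–10% of trials with normal times, roughly 83–93% with skewness near 0.5, and about 99% or more with skewness near 0.8, across by-arm and pooled testing at 0.05. On that route the trial would lose an estimate that the planned t test gives to within about ±3 min. This should be settled before outcome data are examined.

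**What to change.** Add two sentences to section 12, along these lines:

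*The primary analysis is the difference between arms in mean operative time (staple minus suture, in minutes) with its 95% CI and two-sided p value at alpha 0.05, from a Welch two-sample t test or an equivalent linear model, regardless of any normality test. A Mann-Whitney test will be reported as a sensitivity analysis only.*

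The general rule can stay for secondary continuous variables. The same edit should use one name and definition for the outcome, since section 6.6 and section 12 label it differently.

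No extra data are needed, and N stays at 316 evaluable and 352 enrolled. The stated power of 90.2% still applies, because the analysis then matches the calculation.
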